For hypotheses 3A and 3B, the following preprocessing and analytical parameters will be used. Preprocessing: Post-acquisition preprocessing and statistical analysis of imaging data will be performed using FEAT (FMRI Expert Analysis Tool) Version 5.98, part of FSL (FMRIB's Software Library). Data will be preprocessed using scripting tools from FEAT. Non-brain signal will be removed using FSL's BET brain extraction. Scans will be corrected for motion using FSL's linear registration and scans will be spatially smoothed using a Gaussian kernel of 8 mm FWHM. Participants with head motion ≥ 0.2 mm will be excluded from the analyses¹²⁷. Motion artifacts will be identified and scrubbed from each subject's data. Scans will be spatially co-registered with a standardized anatomical template (Montreal Neurological Institute) using a 12 parameter affine transformation. Analysis: Functional connectivity will be measured using a psychophysiologic interaction seed-based approach¹²⁹⁻¹³⁰. PPI analysis is used to assess the functional coupling between different brain regions. The PPI is defined as the change in connectivity of one area (i.e., the seed region) to another in relation to the experimental context (e.g., alcohol vs. neutral cues). PPI analyses for resting state, trauma and alcohol cues will be performed separately. Customized sq. wave forms representing the trauma run (1=trauma block and -1=neutral block) and the alcohol cue run (1=alcohol block and -1=neutral block) the duration of each block will be convolved with a double-gamma hemodynamic response function. A mask of the seed region will be made using a 12-mm diameter sphere located in the center of the AMY using the MNI coordinates (x, y, z = ± 22 , 0, -22). The transformation parameters described above will also be applied to the mask. For each subject, the mean corrected and high pass filtered time series of the BOLD signal in the AMY will be extracted and used in a single subject whole brain PPI analysis. The PPI model will include the task vector, time series of the BOLD signal in the AMY, a term representing the positive task x seed interaction, and a term representing the negative task x seed interaction. The first level analysis will generate contrast images of the parameter estimates for each of the four regressors. Voxels will be thresholded at $Z > 2.3$ using a corrected cluster threshold of $p = 0.05$. The contrast images of the parameter estimates of the positive and negative task x seed interactions will be combined for group-level t-tests to identify regions that exhibited altered connectivity with the AMY during the trauma and alcohol cues as compared to neutral cues. All group-level results will be thresholded at $Z > 2.3$ using a corrected cluster threshold of $p = 0.05$. Separate linear regression tests will be used to test for associations between PFC-AMY connectivity at baseline and improvement in AUD and PTSD symptoms during treatment. Changes in total standard drinks will be regressed against the parameter estimate obtained from the center voxel from each cluster that exhibited a significant task x seed interaction with the AMY at rest and in response to the alcohol cues (Hypothesis 3A). Changes in CAPS-5 total scores will be regressed against the parameter estimate obtained from the center voxel from each cluster that exhibited a significant task x seed interaction with the AMY at rest and in response to the trauma cue (Hypothesis 3B). Further exploratory analyses will examine change in PFC-AMY connectivity from pre- to post-treatment and associations with alcohol and PTSD outcomes, both within and between medication groups.

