
Exploratory Hypothesis 4: NAC treatment will be associated with a significant change in ACC glutamate concentrations, as compared to placebo. Change in ACC glutamate concentrations will be associated with alcohol and PTSD outcomes.

Analysis of PRESS data will be conducted using LC Model 6.3¹³¹, an operator-independent curve-fitting software package that uses least-squares estimation for quantifying metabolite concentrations; the basis set for TE = 40ms is provided by the vendor and includes a number of metabolites including glutamate, creatine, glutamine, N-acetylaspartate, and phosphocholine. Only metabolites with fitting uncertainties (Cramer-Rao Lower Bound values) $< 20\%$ of SD in the LC Model output will be retained for analysis. LC Model includes standardized zero filling, Fourier transformation, and automated phase, baseline and eddy current correction. To address variability in within-voxel tissue composition we will extract and segment T₁-weighted images into partial volume maps of gray matter (GM), white matter (WM), and CSF using FSL tools, match the coordinates and size of the ¹H-MRS voxel with the segmented images and extract the tissue fractions within the voxel, correct the raw values obtained from the LC model (scaled

to water) for CSF and coil loading, and calculate each participant's GM to brain matter (GM/[GM+WM]) ratio for use as a covariate in the analyses. Change in glutamate levels will be analyzed as a mixed model (SAS PROC MIXED) with time as a within subject variable and medication group as between subject variables. Variables known to influence ACC glutamate levels (e.g., age, smoking status, tissue composition) will be considered as covariates. Further exploratory regression analyses will examine associations between glutamate difference scores and clinical outcomes (e.g., change in total standard drinks and CAPS-5 score) both within and between medication groups.

Summary: The proposed study will answer important questions regarding the potential of NAC as an effective pharmacotherapy for AUD and comorbid PTSD, and elucidate possible mechanisms underlying improved outcomes. The findings from this study have the potential to significantly improve the standard of patient care and accelerate research on the treatment of AUD and co-occurring PTSD

REFERENCES

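### Hypotheses 3A and 3B: one outcome regression per significant cluster and state, with no multiplicity adjustment, no cap on clusters and no rule for what counts as support

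*Combined protocol and SAP*

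**What the plan says.** All references are to the Combined protocol and SAP, STATISTICAL ANALYSES.

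- **Hypotheses.** 3A holds that prefrontal–amygdala connectivity, at rest and to alcohol versus neutral cues, predicts reduction in total standard drinks. 3B says the same for rest, trauma cues and CAPS-5.
- **Cluster selection.** Amygdala-seeded analyses over the whole brain are run separately for rest, trauma cue and alcohol cue. Group maps are thresholded at Z above 2.3 with a cluster-corrected p of 0.05.
- **Outcome tests.** "Separate linear regression tests will be used to test for associations between PFC-AMY connectivity at baseline and improvement" in the two clinical outcomes. For 3A, "Changes in total standard drinks will be regressed against the parameter estimate obtained from the center voxel from each cluster" showing a significant "task x seed interaction with the AMY at rest and in response to the alcohol cues (Hypothesis 3A"). The 3B sentence has the same form, with CAPS-5 change and the trauma cue.
- **Status.** The next hypothesis is headed "Exploratory Hypothesis 4: NAC treatment will be associated with a significant change in ACC glutamate concentrations". 3A and 3B carry no such label. Within their analysis text, only the later pre- to post-treatment connectivity analyses are called exploratory.
- **Power.** Under Power and Sample Size, the connectivity calculations use a two-tailed alpha of .05 for a single two-group comparison and expect about 140 of 200 participants in the imaging component.

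**The concern.** Inference here has two stages. The first finds clusters, and the corrected threshold limits false clusters in each map. The second regresses clinical change on the "parameter estimate obtained from the center voxel from each cluster that exhibited a significant task x seed interaction", and this stage is what tests 3A and 3B. The first-stage correction does not carry over. Clusters are chosen without reference to outcome, which avoids circularity, but each one still brings its own outcome test.

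The number of tests is set by how many clusters appear. Nothing says what happens if one regression out of several is significant. One chance result could therefore be reported as the prognostic indicator that Specific Aim 3 seeks, although the power statements assume a single test at 5%.

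**Working it through.** **1. The plan's own figure.** The power statement closest to a prognostic question is the relapse comparison: d = 1.0, two-tailed alpha .05, 80% power, N = 34. A two-sample t-test needs 16.7 per group, so 17 per group and 34 in total (power 0.807). The figure is reproduced, and it is for one test. The companion total of N = 26 for d = 0.8 is not reproduced: 26 is the number per group, so the total is 52. The planned 140 exceeds both totals, so this does not bear on the present point.

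**2. Number of tests.** With c clusters per state and two states (rest and matching cue), each hypothesis has k = 2c regressions. The documents give no value for c. The values c = 1, 2 and 3 are assumptions.

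**3. Chance of at least one false association per hypothesis, each test at 0.05.** For independent tests this is 1 − 0.95^k. For correlated tests it was computed for equally correlated normal test statistics. The correlation is also an assumption.

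| Clusters per state | k | Independent | Correlation 0.5 | Correlation 0.8 |
|---|---|---|---|---|
| 1 | 2 | 1 − 0.95² = 9.75% | 9.1% | 7.8% |
| 2 | 4 | 1 − 0.95⁴ = 18.5% | 15.6% | 11.4% |
| 3 | 6 | 1 − 0.95⁶ = 26.5% | 20.7% | 13.9% |

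A simulation of the regressions themselves agrees. It used N = 140, 4,000 runs per setting and an assumed correlation of 0.3 between the two outcomes. At correlation 0.8 it gave 7.7–8.0%, 11.7–12.4% and 13.3–13.7% for k = 2, 4 and 6. Results at N = 105 were similar.

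**4. Dependence on the success rule.** These figures assume that any significant regression supports the hypothesis. If support required significance in both states, with one cluster per state, the chance of false support could not exceed 5%. The plan states neither rule.

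**5. Price of an adjustment.** The correlation detectable with 80% power is tanh[(z for 1 − alpha/2 + 0.8416)/√(N − 3)]. At N = 140, √137 = 11.705.

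- alpha 0.05: (1.960 + 0.842)/11.705 gives r = 0.235
- alpha 0.025 (first Holm step, 2 tests): (2.241 + 0.842)/11.705 gives r = 0.257
- alpha 0.0125 (first Holm step, 4 tests): (2.498 + 0.842)/11.705 gives r = 0.278

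As a rough guide, d = 0.8 with equal groups corresponds to r = 0.8/√(0.8² + 4) = 0.37. If an effect of that size carried over, power at alpha 0.005 (first Holm step for 10 tests) would be about 0.96 at N = 140. It would be about 0.87 at N = 105, which is 140 × 0.75, borrowing the plan's 25% attrition.

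**The case against.** The strongest reply has four parts.

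- **Size.** No cluster count appears in the documents. A reader might infer that the error rate of each hypothesis is several times 5%. The documents do not support that as a fact: with one cluster per state it is at most about twice 5%, and high correlation between clusters holds it down. This part stands, and the size can only be given as a range.
- **Family of tests.** Both hypotheses name prefrontal–amygdala connectivity, so perhaps only prefrontal clusters count. That is a fair reading and would reduce k. However, the search is whole-brain, no prefrontal region is fixed, and the operative sentences refer to each cluster. Even one prefrontal cluster per state leaves two tests.
- **Success rule.** The hypotheses join rest and cue with the word and. Read as requiring both, they imply no inflation across states. This stands as a possible reading, but the plan does not adopt it, and the regressions are described as separate.
- **Status.** Aim 3 is mechanistic, imaging is not among the primary outcomes, and the MRI portion is optional. A reader might infer from the single exploratory label on Hypothesis 4 that 3A and 3B are confirmatory in the sense of Aims 1 and 2. The documents do not say so. They do present 3A and 3B as predictions and call the study well powered to test its hypotheses, so an error rule is a reasonable expectation.

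A further weakness concerns the count itself. The plan asks for a task-by-seed interaction at rest, where there is no task, so how rest clusters are chosen is undefined.

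**Conclusion.** The concern holds in a limited form. As written, 3A and 3B are each tested by an uncapped set of regressions with no multiplicity adjustment and no stated criterion for support. If any significant regression counts, the false-positive chance per hypothesis runs from about 8–10% at 2 tests to 14–27% at 6. These figures rest on an assumed cluster count and on assumed correlations from 0 to 0.8. They fall if only prefrontal clusters are tested, and a state whose map yields no cluster contributes no test. The consequence is confined to prognostic claims under Aim 3. Nothing here touches the efficacy analyses of Aims 1 and 2.

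**What to change.** Amend the analysis text for Hypotheses 3A and 3B as follows:

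1. Prespecify one prefrontal–amygdala connectivity summary per state, which gives two tests per hypothesis. Failing that, restrict the outcome regressions to clusters within a prefrontal region fixed in advance.
2. Define how the resting-state measure is obtained, since no task contrast exists there.
3. Apply Holm across all regressions within 3A, and separately within 3B.
4. Call a hypothesis supported only if at least one Holm-adjusted p is below 0.05, and report every regression run.

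Holm keeps the error for each hypothesis at or below 5% whatever the number of clusters or their correlation.

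The change needs a few lines of SAP text and no new data. The cost is some power per test: at N = 140 and 80% power, the detectable correlation rises from about 0.235 to 0.257 with two tests, or to 0.278 with four. Participants lost to attrition or to the head-motion exclusion would raise these values further. A fixed prefrontal summary could also miss an effect confined to a small part of the region; whole-brain results can still be reported as exploratory.

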PROTOCOL TITLE: A Randomized Controlled Trial of N-Acetylcysteine for Alcohol Use Disorder and Comorbid PTSD

NCT02966873

November 9, 2019

PROTOCOL TITLE: A Randomized Controlled Trial of N-Acetylcysteine for Alcohol Use Disorder and Comorbid PTSD

The primary objective of the proposed Phase II study is to evaluate the effects of NAC in reducing (1) AUD severity and (2) PTSD symptomatology among individuals (N=200) with current AUD and PTSD. We will also use functional magnetic resonance imaging (fMRI) and proton magnetic resonance spectroscopy (MRS) to investigate the neural circuitry and neurochemistry underlying comorbid AUD/PTSD and prognostic indicators of positive treatment response. Secondary objectives are to evaluate the effects of NAC on impairment in associated areas of functioning (e.g., depression, anxiety, sleep, risky behaviors). In order to accomplish this we will (1) employ an intent-to-treat, double-blind, placebo-controlled randomized controlled trial that will consist of 12 weeks of treatment with NAC (2400 mg per day) or placebo medication; (2) examine standardized, repeated dependent measures of clinical outcomes at baseline, week 6, week 12, and 3-, 6-, and 12-month follow-up; and (3) employ advanced neuroimaging methodologies, a laboratory cue paradigm, and collect biologic measures of alcohol consumption. The following specific aims are proposed:

Specific Aim 1: To determine the efficacy of N-acetylcysteine (NAC), as compared to placebo, in reducing alcohol use severity.

Specific Aim 2: To determine the efficacy of N-acetylcysteine (NAC), as compared to placebo, in reducing PTSD symptomatology.

Specific Aim 3: To use multimodal neuroimaging techniques to investigate the pathophysiology underlying AUD and comorbid PTSD, and prognostic indicators of treatment outcome.

Human Subjects Involvement and Characteristics: A total of 200 adults between the ages of 18 and 70 will be recruited over a 5-year period. The inclusion/exclusion criteria are as follows:

Inclusion Criteria:

1. Male or female; any race or ethnicity; age 18 to 70 years old.
2. Subjects must be able to comprehend English.
3. Meet DSM-5 criteria for current alcohol use disorder (AUD).

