Primary Outcome Measures. The primary outcome measures are described in this section. Information regarding additional measures can be found in Table 1. The primary clinical outcomes include: (1) alcohol use severity (TLFB for alcohol consumption), and (2) PTSD symptom severity (CAPS-5 for clinician-rated and PCL-5 for self-reported symptoms). The TLFB obtains retrospective self-report of alcohol use by using a calendar and memory prompts to stimulate recall¹¹². Quantity and frequency of use are obtained (e.g., total number of standard drink units, percent of days drinking, heavy drinking days as defined as 5 or more drinks for a man or 4 or more drinks for a woman) as well as abstinence (yes/no). The TLFB will assess consumption of alcohol as well as nicotine and other substances for 60 days prior to study entry, weekly during treatment, and at follow-up. The TLFB yields consistently high test-retest reliability and convergent validity with other self-reports and collateral reports¹¹³. The OCDS is a 14-item self-report measure of craving with high internal consistency and concurrent validity and good predictive validity of future drinking¹¹⁴⁻¹¹⁵. The CAPS for DSM-5 is a 30-item structured diagnostic interview and gold standard for assessing PTSD¹¹⁶. The CAPS assesses trauma history and has excellent psychometric properties and diagnostic efficiency¹¹⁷. The PCL for DSM-5 is a 20-item self-report measure that assesses PTSD severity and has excellent psychometric characteristics^{116,118}.

STUDY INTERVENTIONS AND PROCEDURES

Overview. Subjects will be randomized to NAC or placebo, and all subjects will receive cognitive-behavioral therapy (CBT) targeting AUD (12, weekly 60-minute sessions). Note that subjects will not receive any other CBT or treatments during the study. All services received (e.g., self-help groups, case management) will be carefully monitored and tracked at weekly visits.

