General. Baseline clinical and demographic characteristics will be collected and contrasts performed between treatment groups. Continuous and ordinal characteristics will be compared using a Wilcoxon Rank-Sum test statistic. Categorical characteristics will be compared using a Pearson Chi-Square test statistic. Baseline characteristics found to be significantly associated with primary outcome measures will be included as covariates in the analyses. All analyses will be performed on the intent-to-treat sample consisting of all randomized subjects. All analysis will be conducted using SAS v9.3 (SAS Institute, Cary, NC, USA).

Randomization. We will stratify by (1) AUD severity (TLFB) and (2) PTSD severity (CAP-5). Stratified random block randomization will be used to balance the randomization assignment with respect to these strata. The purpose of stratification is to distribute these potential prognostic factors equally across treatment groups.

Power and Sample Size. This study is powered to estimate the efficacy of NAC on the reduction in PTSD symptoms, alcohol use, and craving at the end of the treatment phase (final 3 weeks of treatment). This study builds on a recently completed pilot trial of NAC that assessed efficacy in reduction of PTSD symptomology and craving in a cohort of Veterans with PTSD and substance use disorders. In this promising pilot trial, we observed a clinically significant decrease in CAPS total scores following 8 weeks of treatment with NAC ($\Delta=26.8$) while the placebo response was attenuated ($\Delta=17.1$). Assuming a similar difference in treatment effects in a larger population, we will have 80% power with a type 1 error rate of 5% to detect this difference with 75 participants randomized to each of the two treatment arms (total

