Hypotheses. The hypotheses and statistical approaches for testing each hypothesis are listed below.

Hypothesis 1: NAC treatment will result in significantly greater reduction in AUD severity and craving, as compared to placebo. To test this hypothesis, a mixed effects modeling framework will be specified with the total number of standard drinks consumed and the OCDS total score as the primary outcomes. A Poisson distribution will be assumed with a logarithm link function to assess the effects of NAC treatment and the baseline number of total standard drinks (past 60 days) prior to treatment entry. Over-dispersion due to a wider than expected distribution in discrete count models (from heterogeneity) can have a significant impact on parameter inference, thus when detected, a negative binomial (NB) distribution will be specified. Further, data collected in substance abuse studies often contain a preponderance of zeros, and these zeros in the distribution can be considered sampling zeros in the Poisson process¹²⁵. If this excess is present in the distribution, two-part Hurdle models (Poisson and NB) will be explored¹²⁶⁻¹²⁷. The hurdle part of the model will allow us to estimate the probability of abstinence during the study period (as an odds ratio) while the Poisson/NB portion will allow for the assessment of the risk of an increase in using days beyond zero during the study period (as a risk ratio). Model fit of the Poisson (Hurdle Poisson) model will be compared to the Negative Binomial (Hurdle NB) model by practical examination of the deviance and Pearson chi-square values (Likelihood Ratio) with respect to their degrees of freedom. Baseline alcohol use and craving will be included in pertinent models as covariates. Additional alcohol use outcomes will be assessed: percentage of drinking days (DD) and the number of heavy drinking day (HDD). End of study abstinence will be assessed using logistic regression models. DD and HDD will be assessed using count models.

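### Hypotheses 3A and 4 do not guarantee baseline adjustment of the change in drinks; percentage of drinking days is sent to a count model; and the window for total drinks is not reconciled

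*Combined protocol and SAP*

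**What the plan says.** All references are to the combined protocol and SAP.

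- **Hypothesis 1** takes "the total number of standard drinks consumed and the OCDS total score as the primary outcomes" in a mixed-effects count model that includes "the baseline number of total standard drinks (past 60 days) prior to treatment entry". Baseline alcohol use and craving are to be covariates in the relevant models; that sentence sits under Hypothesis 1.
- **Hypotheses 3A and 3B** relate baseline connectivity to "improvement in AUD and PTSD symptoms during treatment". For drinks, "Changes in total standard drinks will be regressed against the parameter estimate" of each significant cluster. No covariate is named, and nothing says whether totals or daily rates are differenced.
- **Exploratory Hypothesis 4** relates glutamate difference scores to, among other outcomes, change in total drinks. No baseline drinks covariate is named.
- **General** (Statistical Analyses) has a conditional rule: "Baseline characteristics found to be significantly associated with primary outcome measures will be included as covariates in the analyses".
- **Time base for drinks.** Primary Outcome Measures collects the TLFB "for 60 days prior to study entry, weekly during treatment, and at follow-up". Power and Sample Size aims at efficacy "at the end of the treatment phase (final 3 weeks of treatment". Hypothesis 1 describes the hurdle model over the study period, and the objectives give a visit grid "at baseline, week 6, week 12, and 3-, 6-, and 12-month follow-up". No offset or days-observed term appears anywhere, although attrition of about 25% is expected.
- **Additional drinking outcomes.** Hypothesis 1 lists drinking days as a percentage and heavy drinking days as a number, then assigns both to count models. Its hurdle paragraph describes the count part in terms of days of use, although the outcome is drinks.

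**The concern.** Hypothesis 3A asks whether connectivity predicts improvement. Heavier drinkers have more to lose: if everyone cuts down by the same fraction, they show the larger absolute fall. A brain measure that is only correlated with how much a person drinks will then correlate with the change score while saying nothing about who responds. Subtracting totals over unequal numbers of days has the same effect. A person who drinks steadily shows 84/60 − 1 = +40% on an 84-day total against the 60-day baseline, and 21/60 − 1 = −65% on a 21-day total. Baseline adjustment deals with both, but the plan guarantees it only for Hypothesis 1.

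The drinking-days problem is separate. A percentage has no count variance, and a count model without days observed gives someone seen for 7 days the same weight as someone seen for 84.

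The open window leaves room to choose between analyses of a primary outcome after the data are seen.

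**Working it through.** **The plan's own figures.** Allowance for attrition: 75/(1 − 0.25) = 100 per arm, as stated. The claim of at least 80% power for a risk ratio of 0.75 in drinks can be neither confirmed nor refuted, because no control mean, dispersion or window is given. With variance (1/μ + 1/(0.75μ) + 2k)/n, 75 per arm and an assumed 5 drinks per day over 7 to 84 days, 80% power needs a dispersion k of at most about 0.36 to 0.39. Nothing below depends on this.

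**Change scores: why level enters.** Let λ be baseline drinks per day, f the average proportional fall, and T the post-baseline days. Then

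- expected change in raw totals = λ × [T(1 − f) − 60]
- expected change per day = λ × [(1 − f) − 1] = −fλ

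Wherever the multiplier of λ is not zero, the change score contains drinking level.

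**Simulation inputs.** From the plan: n = 140 (expected imaging participants), a 60-day baseline, 12 weeks = 84 days, and the final 3 weeks = 21 days. Assumed: all 140 complete; baseline rate lognormal with mean 5 per day and log-SD 0.8; on-treatment rate = baseline × (1 − f) × mean-1 lognormal noise with log-SD 0.2, 0.6 or 0.8; Poisson totals; connectivity correlated r = 0.2 with log baseline rate and otherwise unrelated to on-treatment drinking; linear regression, two-sided 5%. A false positive means that connectivity is declared predictive although it adds nothing beyond baseline level.

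| Unadjusted change score | Fall f | Multiplier of λ | False positives at noise 0.2 / 0.6 / 0.8 |
|---|---|---|---|
| Raw total, 84 days | 0% | 84 − 60 = +24 | 28 / 10 / 8% |
| Raw total, 84 days | 30% | 58.8 − 60 = −1.2 | 6 / 7 / 6% |
| Raw total, 84 days | 50% | 42 − 60 = −18 | 37 / 15 / 13% |
| Raw total, 21 days | 0% | 21 − 60 = −39 | 54 / 44 / 38% |
| Per day | 0% | 0 | 4 to 9% |
| Per day | 30% | −0.3 | 39 / 15 / 15% |
| Per day | 50% | −0.5 | 51 / 32 / 24% |

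Across all settings tried at r = 0.2, the unadjusted rate runs from about 5% to 57%. With baseline drinks as a covariate it is 4% to 6%. At r = 0 it stays near 5% without adjustment. A second model, with an assumed baseline to follow-up correlation of 0.5 and r = 0.2, gives 59% (21-day total), 21% (60-day) and 8% (84-day) unadjusted, and 4.3% to 5.2% adjusted. So matching the windows does not remove the problem; the covariate does. Hypothesis 4 was not simulated.

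**Percentage as a count.** At 50% drinking days the Poisson variance is 50 whatever the number of days. The binomial variance of the percentage is 10000 × 0.25/n.

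| Days observed | Binomial variance | Poisson SE ÷ binomial SE = √(50/variance) |
|---|---|---|
| 84 | 29.8 | 1.30 |
| 21 | 119 | 0.65 |
| 7 | 357 | 0.37 |

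This takes days as independent, with no between-person spread and no over-dispersion term.

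**Window in Hypothesis 1.** With no effect, no dropout and 75 or 100 per arm, single analyses reject in 4% to 7% of simulated trials. Taking the better of the 84-day and 21-day windows rejects in 8% to 11%. That simulation has not been independently repeated, and it is an upper bound for a free choice.

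**Offset in Hypothesis 1.** If one total per person were modelled and dropouts left at a uniform time, assumed placebo/NAC dropout of 25/25 gives a ratio of 1.00. At 20/30 it is (1 − 0.30/2)/(1 − 0.20/2) = 0.85/0.90 = 0.944.

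**The case against.** The strongest reply is that the general covariate rule already covers the change scores. Total drinks is a primary outcome, the rule sits under a general heading, and baseline drinking is almost certain to be associated with on-treatment drinking: in the simulated data without an average fall it was significant in every run. If the rule reaches these regressions, the covariate comes in. This is fair, and it is why the point is that adjustment is not guaranteed, not that it is excluded. But the rule depends on a significance finding, and the paragraphs for 3A and 4 do not invoke it.

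Second, the size depends on assumptions. The documents give no connectivity-drinking correlation, noise level or average fall, and at zero correlation nothing happens. This stands too. However, every participant receives 12 sessions of CBT for alcohol use, so some average fall is to be expected, and the per-day change is then affected as well.

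Third, the abbreviation for drinking days could be read as a number of days, and the plan switches to a negative binomial if over-dispersion is detected. That would largely address the cases where the Poisson SE is too small (0.65 and 0.37); the 1.30 case is conservative. It does not bring in days observed, and the outcome is listed as a percentage.

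Four stronger readings are tempting but not supported:

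- *The unit of the primary alcohol outcome is undefined.* It is defined: standard drinks, in Primary Outcome Measures and in Hypothesis 1. The phrase about days of use occurs once, in a contingent hurdle model, and does not create a rival primary outcome.
- *No post-baseline window is given.* The power section names one; it is not carried into the analysis text.
- *The inflation comes only from subtracting raw totals.* The table shows the opposite for a 30% fall: the raw 84-day total is nearly clean and the per-day change is not.
- *The Hypothesis 1 treatment ratio is biased.* That needs one total per person and unequal dropout. The plan specifies a mixed model, and weekly rows largely avoid the problem.

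**Conclusion.** The concern holds, mainly as an improvement available at almost no cost.

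1. **Baseline covariate (main point).** Adjustment of the drinks change scores in Hypotheses 3A and 4 is left to a conditional rule that may or may not apply. Under the stated assumptions (n = 140, r = 0.2), leaving it out gives false-positive rates from about 5% to 57%; including it gives 4% to 6%. The size for Hypothesis 4 is not known.
2. **Drinking days.** Sending a percentage to a count model without days observed is wrong as written, whatever window is chosen, and so is the hurdle wording. Planned handling of over-dispersion reduces the practical damage, and these are additional outcomes.
3. **Window.** The power section, Hypothesis 1 and Hypothesis 3A describe different periods. A free choice between 84 and 21 days would put the Hypothesis 1 false-positive rate at about 8% to 11% at most.

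This should be settled before unblinding. It does not show that the primary treatment comparison is biased.

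**What to change.** - **Hypotheses 3A and 4:** analyse change in drinks per day and always include baseline drinks per day as a covariate, whatever the general significance rule gives. Cost: one degree of freedom per regression.
- **Drinking and heavy drinking days:** model days out of days observed with an over-dispersed binomial, or as counts with log(days observed) as an offset. The binomial reports an odds ratio, so state the effect measure. Correct the hurdle text so that its count part models drinks, and account for days observed in the abstinence part.
- **Total drinks:** name one window and time base and use it in the power section, Hypothesis 1 and Hypothesis 3A, for example weekly counts over weeks 1 to 12 with log(days observed) as an offset. With weekly rows the offset matters only for incomplete weeks. It does not correct informative dropout, which needs its own sensitivity analysis.

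The TLFB data are already scheduled, so visits and sample size do not change. The cost is SAP wording and minor programming.
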